Following baseline assessments and identification of main PD stones, patients will be randomly assigned to receive either PPL or ESWL as the primary lithotripsy method to fracture PD stones. Both these procedures represent potential next steps in the algorithm of managing PD stones.³ If partial clearance (removal of some, but not all stones) of PD stones is achieved as determined by the performing endoscopist, subjects can receive repeated PPL or ESWL sessions (for a maximum of 4 sessions total as is commonly practiced before referral for alternative therapy) until complete removal of stones is achieved.⁵ Failure to remove any main PD stones will be considered a failure of the treatment. Additionally, failure to achieve complete clearance within a maximum of 4 sessions of either PPL or ESWL will be considered a treatment failure, even if partial clearance is achieved.

Cross-over and/or combination therapy will be allowed at the discretion of the endoscopist after treatment failure. As described in the statistical analysis, under the intention-to-treat (primary) analysis, should cross-over occur, the final outcome of complete stone clearance will be attributed to the initial therapy. Under the per-protocol (secondary) analysis, in the case of cross-over, the final outcome of complete stone clearance will be attributed to the combination of ESWL and PPL. Similarly, in terms of survey collection, should cross-over occur, the analysis of the survey results will be attributed to the

originally assigned intervention in the intention-to-treat (primary) analysis. In the per-protocol (secondary) analysis, the outcomes will be attributed to the combination of both interventions resulting in technical success.

Patients who are randomized and subsequently found to have an exclusion criteria identified will continue follow-up per study protocol.

Stone clearance will be determined by occlusion pancreatography showing the absence of main PD stones. Complete stone clearance will be defined as the absence of stones in the head or body of the main PD. Partial stone clearance will be defined as the removal of more than 50% but less than 100% of stone/stone fragments in the head or body of the main PD.

[figure not shown]
Recurrence will be defined as the presence of stones following confirmed clearance in the final pancreatogram. To be considered as recurring, the stone must require intraductal lithotripsy for removal.

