Statistical Analysis: Comparison of technical success rate, defined as the rate of complete clearance of PD stones, between PPL and ESWL will be performing using the chi-squared test or Fisher's exact test. Secondary outcomes including adverse event (both overall and serious adverse event) rates, procedure length, and number of procedures will be compared using a chi-square test or Fisher's exact test for categorical variables and the Student's t test will for continuous variables. A p value <0.05 will be considered significant. In the primary analysis, all results will be analyzed under an intention-to-treat protocol. A per-protocol (secondary) analysis will also be performed where the technical success will be attributed to the combination of modalities resulting in achieving the primary outcome should cross-over occur.

To identify predictors for technical success, a multivariable logistic regression will be performed incorporating variables that were associated ($p<0.2$) with technical success on univariate analysis.

In terms of secondary outcomes, change in PANQOLI scores, VAS scores, and opiate daily doses will be compared between subjects in the PPL group and ESWL group. Additional outcomes to be measured include stone recurrences and number of chronic pancreatitis-related hospitalizations during the follow-up period. Should cross- over occur, under the primary (intention-to-treat) analysis, the outcomes will be attributed to the initially randomized intervention. In the secondary (per-protocol) analysis, the outcomes will be attributed to the combination of treatments resulting in technical success. A subgroup analysis will also be performed on patients who achieved only partial stone clearance (thus considered a treatment

failure) in the above-mentioned outcomes. Comparisons will be made using a chi-squared test or Fisher's exact test for categorical variables and the Student's t test for continuous variables. Paired t tests will be performed to evaluate individual changes within each arm. A p value <0.05 will be considered significant.

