The most common AEs for PPL are expected to include pancreatitis and bleeding. The most common infectious complications are expected to include cholangitis, cholecystitis, and less likely or rare duodenoscope-related infection transmissions and perforation. No differences in the types and proportion of AEs have been found in previous studies examining EHL and LL.¹⁰

The risks of ESWL include post-ESWL pancreatitis, bleeding, infection, steinstrasse, sepsis, and rarely, perforation, pancreatic duct leak and arrhythmias. An overall AE rate for ESWL is 6.7%.²¹ The most common adverse event associated with ESWL remains pancreatitis with a meta-analysis finding a rate of 4.2%.¹⁴ Mild skin erythema and tenderness also typically occurs at the region of contact with the shockwaves and other adverse events such as bleeding and infection occur in approximately 1% of cases.³ Similarly, the primary risk of PPL is pancreatitis which in a meta-analysis was found to occur in 8.7% of cases.¹⁵ Additional risks include incomplete fragmentation of the stone requiring alternative treatment,

stone migration, inability to access stones(s), no stones, need for further procedures, loss of pancreas and/or death. Machine malfunction may occur, necessitating rescheduling. In addition, the stones might not get removed completely. In comparison, surgery, an alternative treatment modality typically consisting of either a lateral pancreaticojejunostomy or a Frey procedure, has a higher rate of adverse events. In a randomized trial comparing surgery with endoscopy, the surgical treatment arm had a 27% adverse event rate with the main adverse events including anastomotic leakage (6.8%), bleeding (6.8%), incisional hernia (4.5%), pneumonia (4.5%), and severe delayed gastric emptying (4.5%).²² Additionally, as these procedures would typically be performed as part of the management of patients with PD stones at the study sites, there are no separate research risks from the risks of standard care.

Worsening abdominal pain may occur after either of the procedures, with the potential need for prolonged observation. Abdominal pain may be related to ductal manipulation, stone mobility, or due to other adverse events.

The definition of a serious AE is any AE that results in any of the following outcomes:

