All serious AEs that occur from initiation of the study to 14 days post final intervention are to be reported immediately (within 24 hours) using the electronic data collection system. All serious AEs will then be immediately relayed to the PIs. The PIs will first review the AEs to: 1) ascertain the seriousness, 2) ascertain the relationship between AE and intervention, 3) verify that all data are complete, and 4) follow-up with the specific site for incomplete data and/or data clarification. The PIs will then submit the AEs to the DSMB, who will then review the AEs to confirm the findings of the PIs.

All AEs from ESWL are ESWL-related. PPL is part of the ERCP procedure. Most AEs in this group will be related to the ERCP procedure itself. A potential rare AE specific to PPL (EHL or LL) is ductal perforation from the lithotripsy fiber and will be noted by the investigator. The investigator will determine the relationship of an AE specific to a lithotripsy device used to fragment the stones.

10.3 *Monitoring of Data*

The DSMB will be responsible for data and safety monitoring. All primary and secondary outcomes as well as data integrity and study progress along with all AEs will be reviewed by the DSMB.

The DSMB will meet at least twice a year to review the data mentioned above. These meetings will every six months.

An interim analysis will be performed at the halfway point of enrollment, which is expected to be at the 75th patient. Should the interim analysis reveal an unexpected accumulation of AEs or a clear superiority of one lithotripsy method over the other, the DSMB may recommend stopping the study, which will be reported to the PIs, IRB and the funding agency.

The DSMB will include at a minimum the following individuals:

- [name]: Gastroenterologist, University of Colorado
- [name]: Hepatologist, University of Colorado
- Biostatistician: Non-study Statistician
- [name]: Gastroenterologist, Beth Israel Deaconess Medical Center

11. Feasibility/Recruitment Plan/Materials

The power analysis suggests that a total of 150 participants will need to be enrolled to achieve sufficient statistical power to compare the two lithotripsy methods. With a total of 8 recruitment sites, we anticipate complete enrollment within 5 years and with a follow-up of 12 months/patient post completion of treatment, the study is anticipated to be completed within 6 years.

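### Adverse events are compared only by randomised arm although cross-over is allowed after failure, so no planned analysis isolates the harm of each therapy

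*Combined protocol and SAP*

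**What the plan says.** Section 9 (Data Analysis Plan) covers AEs explicitly: "Secondary outcomes including adverse event (both overall and serious adverse event) rates, procedure length, and number of procedures will be compared", by chi-squared or Fisher's exact test for categorical variables. It then sets the rule for the main analysis: "In the primary analysis, all results will be analyzed under an intention-to-treat protocol". AEs are not exempted. For the patient-reported, opiate and recurrence outcomes the section repeats that, after cross-over, "under the primary (intention-to-treat) analysis, the outcomes will be attributed to the initially randomized intervention".

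Section 3 (Sample and Methodology) sets the cross-over rule: "Cross-over and/or combination therapy will be allowed at the discretion of the endoscopist after treatment failure". No expected cross-over rate is given anywhere.

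The secondary per-protocol analysis in Section 9 is one "where the technical success will be attributed to the combination of modalities resulting in achieving the primary outcome should cross-over occur". Neither it nor the parallel sentence for the other secondary outcomes mentions AEs.

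Section 10.2 has a rule for expedited reporting that covers "All serious AEs that occur from initiation of the study to 14 days post final intervention". It also provides for attribution: "The investigator will determine the relationship of an AE specific to a lithotripsy device used to fragment the stones". The synopsis lists therapy-related AEs as a secondary endpoint.

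**The concern.** An AE table by randomised arm answers one question: how much harm follows from starting with PPL or with ESWL, including whatever is done after failure. The synopsis endpoint asks another: how much harm comes from each therapy. Once patients can receive both, the two answers differ, and the plan provides only for the first.

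The mixing is not symmetric. The planning figures expect more failures under ESWL than under PPL, so more PPL events should enter the ESWL arm than ESWL events enter the PPL arm. PPL also carries the higher cited pancreatitis rate; Section 10.1 says "the primary risk of PPL is pancreatitis which in a meta-analysis was found to occur in 8.7% of cases", against 4.2% for ESWL. Both features pull the observed difference towards zero. At stake is the estimate of comparative harm, in the final report and in any table by randomised arm that the DSMB uses when it considers AEs.

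**Working it through.** **Where the failure rates come from.** Section 9 plans on complete clearance of 70% (ESWL) and 90% (PPL), two-sided alpha 0.05 and 80% power. With pooled variance and no continuity correction:

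n = [1.96·√(2·0.80·0.20) + 0.8416·√(0.70·0.30 + 0.90·0.10)]² / 0.20² = (1.1087 + 0.4610)² / 0.04 = 61.6, so 62 per arm.

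This reproduces the plan's 62. The same assumptions imply failure in 30% of ESWL and 10% of PPL patients.

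**Other inputs.** Pancreatitis is 4.2% for ESWL and 8.7% for PPL (Section 10.1), with 75 patients per arm (Section 9). The share of failures who cross over, c, is not in the documents and is varied from 0 to 1.

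**Assumptions.** The cited rates are per-patient risks for each therapy, the risks are independent, and a patient who crosses over has the same risk from the second therapy as a first-line patient.

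**Rates by randomised arm.**

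- ESWL arm: 1 − (1 − 0.042)(1 − 0.30·c·0.087)
- PPL arm: 1 − (1 − 0.087)(1 − 0.10·c·0.042)

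| c | ESWL arm | PPL arm | Difference (points) | Shrinkage |
|---|---|---|---|---|
| 0 | 4.20% | 8.70% | 4.5 | 0% |
| 0.25 | 4.83% | 8.80% | 4.0 | 12% |
| 0.50 | 5.45% | 8.89% | 3.4 | 24% |
| 0.75 | 6.08% | 8.99% | 2.9 | 35% |
| 1 | 6.70% | 9.08% | 2.4 | 47% |

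**Sensitivity to PPL clearance.** The documents also give 86% (Section 1) and a range of 83–99% (Section 9). With every failure crossing over, shrinkage is 44% at 86%, 41% at 83% and 55% at 99%. It is 56% if all ESWL failures and no PPL failures cross over. With half crossing over, it is 21–28% across these cases. The ratio of failures, ESWL to PPL, is 30/10 = 3 on the planning value, 30/14 = 2.1 at 86% and 30/17 = 1.8 at 83%.

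**In patients.** Without cross-over the ESWL arm expects 75 × 0.042 = 3.2 pancreatitis cases. Full cross-over adds 75 × 0.30 × 0.087 = 2.0 from PPL, and half cross-over adds about 1.0. The reverse flow at full cross-over is 75 × 0.10 × 0.042 = 0.3.

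**Power.** With 75 per arm, power to detect 4.2% against 8.7% is about 20% (exact Fisher 11%) with no cross-over and about 8% (Fisher 4%) with full cross-over.

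**Do the existing provisions fill the gap?**

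- The per-protocol sentences do not name AEs. They assign patients to the combination that led to technical success, so a patient who crosses over and still fails has no group.
- The device attribution in Section 10.2 feeds no planned comparison. It is also uneven: all AEs of ESWL are taken as ESWL-related, while most in the PPL group are expected to be put down to the ERCP. Filtering on that field would not treat the two therapies alike.

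**The case against.** The strongest objection is that intention-to-treat is right here. Harm from rescue after a failed ESWL course is a real consequence of choosing ESWL first, and only the comparison by randomised arm is protected by randomisation. A comparison cut at cross-over stops counting earlier in the arm with more failures. This stands. It rules out replacing the intention-to-treat table, but not adding a second one.

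A reader might infer that the safety difference will be roughly halved. The documents do not support that. It needs nearly every failure to cross over, whereas cross-over is discretionary, comes only after treatment failure, and competes with other routes such as surgery.

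Nor is 4.5 points an established difference free of mixing. The two rates come from separate meta-analyses whose denominators are not stated. Each therapy may take up to four sessions, and ESWL patients also undergo ERP, whose risk may or may not be in the 4.2%. The planned endpoints, overall and serious AEs, cannot be worked out at all: no overall PPL rate and no serious-AE rate for either arm is given.

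The serious-AE sentence in Section 10.2 might be read as proof that events after cross-over are captured for analysis. It is a reporting deadline, and it does not say whether cross-over procedures count as the last intervention.

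It is also fair that a per-protocol AE table, if one were planned, would take crossed-over patients out of the single-therapy groups and, under the independence assumption, recover 4.2% and 8.7%. But AEs are not named there, and setting crossed-over failures aside selects patients on outcome.

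Finally, the AE test has little power in any case. Dilution therefore affects the estimate more than the test result, and in a trial of this size the safety message rests on the estimate.

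**Conclusion.** The gap is real and worth closing. AEs are compared only by randomised arm, cross-over is open after failure, and no planned analysis isolates the therapy-related AEs named in the synopsis. The intention-to-treat comparison is not an error; it answers a different question, and under the planning assumptions it pulls the therapy-specific difference towards zero.

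The size is uncertain because the cross-over rate is unknown. For pancreatitis alone, the illustrative loss runs from about 0.5 of 4.5 points (a quarter of failures crossing over) to about 2.1 points (all of them). The upper figure, 47%, is near the ceiling and amounts to about two extra cases in the ESWL arm. These figures rest on per-patient, independent risks that are unchanged after failure, and on failure of 30% and 10%. They do not carry over to overall or serious AEs.

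**What to change.** Keep the intention-to-treat AE comparison and add one paragraph to Section 9:

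- Prespecify a supplementary comparison of overall and serious AEs among patients who received their assigned therapy, grouped by that therapy. Count events from the first assigned-therapy procedure to the start of any cross-over or combination therapy.
- State when counting ends for patients who never cross over, since the plan defines no analysis window for AEs.
- Tabulate later events separately, by the therapy given.
- Provide both tables to the DSMB.

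In Section 10.2, state whether the last intervention in the serious-AE reporting rule includes cross-over procedures.

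The cost is small: a paragraph, one clarified definition, and a cut on procedure and event dates that the trial should already hold. It needs no extra patients or visits. The downside is that AE follow-up in the added comparison ends earlier in patients who cross over, more often in the ESWL arm. It should therefore be labelled supplementary and read beside the intention-to-treat table.

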COMIRB 19-0402

PI: [name]

Version Date: December 6, 2023

SARC Approved 5/8/2019

***Per-oral Pancreatoscopy-guided Lithotripsy vs. Extracorporeal Shock Wave
Lithotripsy For Treating Symptomatic Main Pancreatic Duct Stones in Chronic
Pancreatitis: A Multicenter Randomized Clinical Trial***

Lead Site: University of Colorado

Version Date: December 6, 2023

Table of Contents

Table of Contents.....	2
Synopsis	3
List of Abbreviations	4
Study Protocol.....	5
Research Questions and Hypothesis	5
Basic Design of the Study	7
Sample and Methodology	7
Subject Inclusion and Exclusion Criteria	9
Inclusion Criteria:	9
Exclusion Criteria:	9
Study Steps	10
Screening/Baseline Evaluation	10
Consent	10
Randomization	10
Treatment Regimens	10
Outcome Determination	11
Standard of Care/Research Procedure.....	12
Subject and Study Stopping Criteria.....	12
Data Collection Tool	13
Data Analysis Plan	13
Data and safety monitoring plan.....	14
Definition of AEs, serious AEs, and unanticipated problems	14
Procedures for documentation of adverse events	15
Monitoring of Data	16
Feasibility/Recruitment Plan/Materials	16
Training Plan.....	16

Synopsis

Title	Per-oral Pancreatoscopy-guided Lithotripsy vs. Extracorporeal Shock Wave Lithotripsy in Chronic Pancreatitis: A Multicenter Randomized Clinical Trial
Investigative sites	University of Colorado The Ohio State University Baylor St. Luke's Medical Center Methodist Dallas Medical Center University of Minnesota University Health, San Antonio Indiana University Washington University School of Medicine
Hypothesis	The central hypothesis is that per-oral pancreatoscopy- guided lithotripsy is superior to extracorporeal shock wave lithotripsy in clearance of main pancreatic duct stones, thereby improving pain levels and quality of life in patients with chronic calcific pancreatitis.
Primary Objective	To demonstrate the superiority of per-oral pancreatoscopy over extracorporeal shock wave lithotripsy in clearance of main pancreatic duct stones in patients with chronic pancreatitis. Failure to remove any or all stones with the initial intervention will be an outcome recorded for the study.
Secondary Objective	To demonstrate the effect of stone clearance to reduce pain and opiate use and improve quality of life.
Timeline	Enrollment will be performed over a 24-month time period with follow-up performed at 1, 3, 6, 12, 18, and 24 months after ductal clearance.

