This study is a multicenter randomized trial comparing per oral pancreatoscopy-guided lithotripsy (**PPL**) using either laser lithotripsy (**LL**) or electrohydraulic lithotripsy (**EHL**) with extracorporeal shock wave lithotripsy (**ESWL**) in removing main pancreatic duct (**PD**) stones from patients with chronic calcific pancreatitis. Specific aims for this trial include:

- **SA1:** To determine whether PPL is more effective than ESWL in removing PD stones in terms of main pancreatic duct stone clearance rate in patients with chronic calcific pancreatitis.
- **SA2:** Evaluate the effectiveness of main pancreatic duct stone removal in reducing pain and improving quality of life in patients with chronic calcific pancreatitis.
 - **SA2a:** To determine whether a greater clearance of PD stones via PPL or ESWL will improve quality of life to a greater extent.
 - **SA2b:** To determine whether a greater clearance of PD stones via PPL or ESWL will reduce pain and opiate requirements to a larger extent.

The primary endpoint of this trial will be complete clearance of main PD stones in eligible patients. This study will be statistically powered to detect superiority of PPL over ESWL in this primary endpoint. Major secondary endpoints will include: 1) change in quality of life after PD stone removal; 2) change in pain levels after PD stone removal; 3) change in opiate use after PD stone removal; 4) comparison of total number of procedures in both arms, and 5) PD stone recurrence rate.

3. Sample and Methodology

We will enroll 150 subjects (**Figure 1**) with chronic pancreatitis who have symptomatic main PD stones identified by non-invasive imaging, endoscopic ultrasound or prior endoscopic retrograde pancreatography (**ERP**).

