Following complete PD stone removal, patients will be given a validated quality-of-life instrument, the PANQOL¹⁸, at 1, 3, 6, 12, 18, and 24 months post-treatment. Similarly, the visual analog scale will also be given at 1, 3, 6, 12, 18, and 24 months post-treatment. Lastly, daily opiate use will be recorded at 1, 3, 6, 12, 18, and 24 months post-treatment. The 1, 3, 6, 12, 18, and 24-month assessments will have a ± 2 weeks window to be completed.

In order to ensure that subjects respond to the questionnaires as required, REDCap will be programmed to automatically send three reminders to the participants' email when the questionnaires are due. Furthermore, the study coordinator will make three separate attempts to contact non-responding patients within the designated timeframe. If a patient remains unresponsive, these instances will be documented as protocol deviations.

Documentation on interventions for chronic pancreatitis occurring outside of scheduled appointments will be recorded a separate CRF ("non-scheduled chronic pancreatitis interventions"). This CRF will encompass any pancreatic interventions (other than POP x ESWL planned visits) taking place between the subject's consent form signature and their final follow-up.

All patients will have a HgbA1c and fecal elastase drawn at baseline (within 12 months prior to treatment initiation) and at the 1-year mark from treatment completion. Laboratory tests will be drawn per standard of care, and tests results will be added to the REDCap database.

Figure 1: Study Flowsheet

4. Subject Inclusion and Exclusion Criteria

4.1 *Inclusion Criteria:*

1. Subjects aged 18-89
2. Subjects with abdominal pain secondary to chronic calcific pancreatitis and main pancreatic duct stones found on cross-sectional imaging, EUS, or ERP with upstream PD dilation
3. Main PD stones in the head or body that are greater than 50% in size of the immediate downstream diameter of the pancreatic duct
4. Stones ≥ 5 mm in diameter or impacted in the main PD on cross-sectional imaging or EUS

4.2 *Exclusion Criteria:*

1. Subjects who have previously received PPL or ESWL for PD stones within 12 months of enrollment
2. Patients with PD stones isolated in the tail or side branches of the main duct
3. Pancreatic tail stones comprising more than one-third of the stone burden within the main PD, if multiple locations of stones are noted within the main PD
4. Nontraversable ansa loop with upstream stones

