5. Inability to place a transpapillary pancreatic duct stent during ERP
6. Patients with prior pancreatic surgery or surgically altered gastroduodenal anatomy, such as Roux-en-Y surgery

7. Acquired pancreas divisum
8. Significant cardiopulmonary co-morbidities precluding general anesthesia
9. Patients with coagulation disorders that cannot be corrected to an INR below 2.0
10. Patients with ongoing alcohol abuse and/or illicit drug use, except products containing THC
11. Pregnancy
12. Patients in active treatment for malignancy other than non-melanoma skin cancer or papillary thyroid cancer

5. Study Steps

5.1 *Screening/Baseline Evaluation*

Potential eligible patients will undergo an initial visit in which eligibility will be confirmed and the trial protocol explained in detail. All willing and eligible patients providing informed consent will have baseline data obtained including detailed history of chronic pancreatitis (i.e. disease duration, etiology, drug use, and family history of pancreatic disease), endoscopy history, and current medication use. Baseline quality of life and pain levels will also be obtained. Laboratory tests: HbA1c and Fecal elastase will be drawn per standard of care within 12 months prior to enrollment, and tests results will be documented in the study.

The National Institute of Alcohol Abuse and Alcoholism (NIAAA) defines binge drinking as a pattern of drinking alcohol that brings blood alcohol concentration (BAC) to 0.08 percent - or 0.08 grams of alcohol per deciliter - or higher. For a typical adult, this pattern corresponds to consuming 5 or more drinks (male), or 4 or more drinks (female), in about 2 hours.¹⁹

Patients of childbearing potential will undergo a serum/urine pregnancy test based on each site practice, as per the standard of care.

5.2 *Consent*

Patients will be provided the necessary information regarding the study and consent will be obtained either in person and/or electronically through medical records depending on specific site IRB approval guidelines. Consent for the study will be obtained by a member of the study team either in person or electronically through medical records depending on specific site IRB approval guidelines.

5.3 *Randomization*

Randomization will occur after informed consent is obtained and prior to receiving lithotripsy. Once enrolled, the research coordinator will enter the patient into the REDCap database, at which randomization will occur via computer algorithm.

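### Change in PANQOL and VAS is compared between arms with an unadjusted t test although both baselines are collected; baseline-adjusted ANCOVA would usually be more precise at almost no cost

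*Combined protocol and SAP*

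**What the plan says.** All references are to the combined protocol and SAP.

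- **Test.** Section 9 states that "change in PANQOLI scores, VAS scores, and opiate daily doses will be compared between subjects in the PPL group and ESWL group", and prescribes "the Student's t test for continuous variables. Paired t tests will be performed to evaluate individual changes within each arm". No covariate is named for these outcomes. The only multivariable model in the section is a logistic regression for predictors of technical success, which is a different outcome.
- **Baselines.** Section 5.1 states: "Baseline quality of life and pain levels will also be obtained". It does not list a baseline daily opiate dose. The nearest item is "endoscopy history, and current medication use".
- **Visits.** Section 3 schedules PANQOL, VAS and opiate use at six times (for opiates: "daily opiate use will be recorded at 1, 3, 6, 12, 18, and 24 months post-treatment"). Section 9 does not say which visit supplies the between-arm contrast.
- **Follow-up length.** The Synopsis gives "follow-up performed at 1, 3, 6, 12, 18, and 24 months after ductal clearance", and Section 3 also runs to 24 months. Section 11 gives 12 months per patient. Section 7 says the study will be stopped once the sample size is reached and 6-month follow-up is in hand.
- **Who is surveyed.** Section 3 ties the PANQOL to complete stone removal. Section 9 plans an intention-to-treat analysis and a subgroup of patients with partial clearance only.
- **Power.** The power analysis in Section 9 covers stone clearance only. No SD, correlation or effect size is given for PANQOL, VAS or opiate dose.

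**The concern.** Pain and quality of life are the subject of Specific Aim 2 and part of the central hypothesis, but no sample size was calculated for them. Whatever precision these comparisons have depends on how the analysis uses the patients recruited for the clearance endpoint. A change score subtracts the whole baseline value, whether or not baseline predicts follow-up that strongly. When the correlation is moderate, this adds noise. It also over-corrects for chance baseline differences: the arm that happens to start worse will tend to show the larger improvement through regression to the mean. Section 5.3 describes 1:1 allocation by computer algorithm and names no stratification on pain or quality of life, so such imbalance is left to chance.

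At stake is the chance of detecting a real difference in pain or quality of life between the two lithotripsy methods.

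**Working it through.** **1. The plan's own figure.** Inputs from the power analysis in Section 9: clearance 70% and 90%, two-sided 0.05, 80% power. With the pooled-variance formula, n per arm = [1.960 × √(2 × 0.8 × 0.2) + 0.842 × √(0.7 × 0.3 + 0.9 × 0.1)]² / 0.2² = (1.109 + 0.461)² / 0.04 = 61.6, so 62 per arm and 124 in total. This reproduces the plan, and 62 per arm is used below.

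**2. Variance formulas.** Let k = baseline SD / follow-up SD and ρ = the baseline-to-follow-up correlation. In units of the follow-up variance, per patient:

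- change score: 1 + k² − 2ρk
- ANCOVA on baseline (large sample): 1 − ρ²
- difference: (k − ρ)², which is never negative and is zero only when k = ρ.

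**3. Variance ratio, ANCOVA / t test on change.** The documents give neither ρ nor k, so both are assumed.

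| k | ρ = 0.3 | ρ = 0.5 | ρ = 0.7 |
|---|---|---|---|
| 1.0 | 0.91/1.40 = 0.65 | 0.75/1.00 = 0.75 | 0.51/0.60 = 0.85 |
| 0.7 | 0.91/1.07 = 0.85 | 0.75/0.79 = 0.95 | 0.51/0.51 = 1.00 |
| 1.3 | 0.91/1.91 = 0.48 | 0.75/1.39 = 0.54 | 0.51/0.87 = 0.59 |

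Estimating the baseline slope multiplies each ratio by (N − 3)/(N − 4) = 121/120 = 1.008 at N = 124. The worst case in the table then becomes 1.008, a loss of about 1%.

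**4. Power.** Noncentral t, 62 per arm, two-sided 0.05, k = 1, assumed true difference of 0.5 follow-up SD:

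| ρ | t test on change | ANCOVA |
|---|---|---|
| 0.3 | 65% | 82% |
| 0.5 | 79% | 89% |
| 0.7 | 95% | 97% |

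In 20,000 simulated trials per setting with complete outcomes, both tests rejected a true null in about 5% of trials, and the powers agreed with the table to about one point.

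**5. Chance imbalance.** With k = 1, one standard error of the baseline difference is √(2/62) = 0.18 SD. An imbalance of that size shifts the change-score estimate by (1 − ρ) × 0.18 = 0.13, 0.09 and 0.05 SD at ρ = 0.3, 0.5 and 0.7. ANCOVA removes the shift.

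**6. Limit of the remedy.** Steps 2 to 5 assume that outcomes are collected on randomised groups. Suppose instead that only cleared patients are surveyed, at 90% and 70% of 62 per arm, with k = 1, ρ = 0.5, no arm effect, and clearance linked to the follow-up score by an assumed latent correlation of 0.5 or 0.7. In 8,000 simulated trials per setting, the false positive rate was about 7% and 8% for the t test and about 10% and 17% for ANCOVA. This illustrates a mechanism and does not predict this trial.

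**The case against.** The strongest reply is that this is a preference. The t test is valid, the endpoints are secondary and were never powered, and every benefit figure rests on assumed correlations and SDs. All of that stands, and it fixes the grade of the point as an efficiency improvement. The case for acting is the asymmetry: a variance reduction of up to about half against a loss of about 1% in the cases computed, with no new data needed for PANQOL and VAS.

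Several stronger readings are tempting, and the documents do not support them.

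- *The planned test is biased or inflates type I error.* With outcomes on all randomised patients it does neither on average.
- *An overall false positive rate can be attached to these outcomes.* Section 9 names no visit and calls p < 0.05 significant, but no document states how many tests will be run. Nor is the family of endpoints fixed: Section 2 ends its list with "4) comparison of total number of procedures in both arms, and 5) PD stone recurrence rate", while the Synopsis lists adverse events and not recurrence. The unnamed visit and the status of these p values are missing detail, and no error rate follows from them.
- *The time origin is undefined.* For cleared patients, the Synopsis and Section 3 describe essentially the same moment. It is unclear only for patients who are never cleared.
- *ANCOVA would sharpen a comparison restricted to cleared patients.* That group is selected after randomisation and differently by arm. Step 6 shows that adjustment can make the error worse, so no power should be quoted for it.
- *The same gain applies to opiate dose.* The baseline dose is only implied, and the variance formulas do not carry over to doses that are skewed or often zero.

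**Conclusion.** The point holds for PANQOL and VAS. The plan compares change without baseline adjustment although both baselines are to be collected. On the assumptions shown, ANCOVA reduces the variance of the arm contrast by 35%, 25% and 15% at correlations of 0.3, 0.5 and 0.7 with equal SDs. For a 0.5 SD difference that is roughly 18, 10 and 2 to 3 percentage points of power. The gain shrinks to nothing when baseline SD / follow-up SD equals the correlation. The textual finding is secure; the size of the benefit is not known from the documents. It also rests on the baseline measures in Section 5.1 being the PANQOL and the VAS, which the planned change scores require but the section does not name.

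Separately, the follow-up lengths in the Synopsis and Sections 3, 7 and 11 conflict, and no visit can sensibly be named until they are reconciled. The primary endpoint, its test and its sample size are untouched.

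**What to change.** 1. In Section 9, for PANQOL and VAS, replace the between-arm t test on change with ANCOVA: follow-up score as outcome, assigned arm as factor, baseline score as covariate. State in Section 5.1 that the baseline instruments are the PANQOL and the VAS.
2. Reconcile the follow-up length across the Synopsis and Sections 3, 7 and 11. Then name one visit for the contrast that every patient is due to reach under the reconciled text.
3. Collect these outcomes by assigned arm from cleared and uncleared patients, on a time origin that exists for both, and amend Section 3 to say so. Without this, the ANCOVA in item 1 does not compare the randomised groups.
4. Extend the adjustment to daily opiate dose only if a baseline daily dose is confirmed as recorded or extractable, and use a model suited to skewed or zero-heavy data.
5. The paired within-arm tests may stay as description in support of the secondary objective ("To demonstrate the effect of stone clearance to reduce pain and opiate use and improve quality of life").

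**Cost.** Items 1 and 2 are wording plus a standard procedure in the SAS software named in Section 8, with no new baseline data for PANQOL and VAS. Item 3 may mean surveying treatment failures who would otherwise not be surveyed. Item 4 may need extraction from medication records. The changes should be made before comparative results are seen.
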